For Veterans, the intervention will target Caregiver participation in home-based Veteran mobility activities. Outcomes for Veterans will include the timed up and go test (TUGT), Expanded Disability Status Scale (EDSS), self-efficacy, fatigue, and depression. MS Caregivers report high burden, stress, and depression involved in caring for their loved ones, especially as mobility declines (3-5) and these outcomes are related to physical and emotional health status of the patient (2). For Caregivers, the intervention will focus on improving Caregiver coping and on managing MS-related problems. Outcomes for Caregivers will include depression, burden, anxiety, and number of Veteran MS problems and safety alerts reported, measured at baseline, End of Intervention (3 months), and 6 months.

Study Objectives include:

- 1) Test whether a caregiver intervention can be integrated into an MS clinical setting.
- 2) Determine whether Caregiver outcomes are improved.
- 3) Determine whether Veteran outcomes are improved.
- 4) Determine which types of Caregivers will benefit most.
- 5) Determine which types of Veterans will benefit most.
- 6) Refine materials for future clinical research, translation and implementation.

HYPOTHESES

Hypotheses are related to both Veteran and Caregiver:

Hypothesis 1: Veterans of Caregivers who receive the intervention will have significant improvement in outcomes including the Expanded Disability Status Scale (EDSS), the timed up and go test (TUGT), self-efficacy, fatigue, impact on daily life, and depression.

Hypothesis 2: Caregiver participants will have significant improvement in outcomes including depression, burden, anxiety, and number of Veteran MS problems and safety alerts reported.

[figure not shown]
RESEARCH METHODS

Caregivers of Veterans with MS will receive a behavioral caregiver intervention designed to address caregiver coping and management of patient concerns, with special focus on patient mobility and walking. A pre-post intervention design will compare outcomes for Veterans and Caregivers. Veterans will complete mobility assessments and answer questions about their health and well-being.

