Caregiver depression is associated with greater MS disease severity, poorer veteran health, and perceived social support (21). Conversely, MS patients with supportive caregivers report better adherence to medication regimens and disease modifying therapies (22). Quality of life decreases in MS patients whose caregivers are depressed and lack social support (21). Providing caregivers with education, coping skills, problem solving and support can help increase quality of life for both the caregiver and care recipient (23,24). Providing skills for managing mobility and including caregivers in the treatment plan may help caregivers perform their tasks while avoiding injury to themselves and the MS patient (1). The Caregiver's efforts to help the Veteran improve physical activity may result in maintaining a level of independence for a greater period of time, thus reducing the need for care (1).

Caregiving Interventions. Successful caregiving interventions target skills MS caregivers need: problem solving, cognitive reframing, stress management, and communication to manage patient concerns/behaviors and their own stress and coping (6,25). The REACH VA intervention is based on Resources for Enhancing Alzheimer's Caregivers Health (REACH II) (6) and Resources for Enhancing All Caregivers' Health in VA (REACH VA) (7-8). With Public Law 111-163 Caregivers and Veterans Omnibus Health Services Act of 2010, REACH VA became a VA clinical program for dementia and SCI/D Caregivers and, in 2015, will include materials for PTSD, MS, and ALS

Caregivers. REACH has also been successfully used with SCI caregivers outside VA (9) in a research design where caregivers and patients both received services.

The REACH intervention provides caregivers with tools and skills to manage ongoing and evolving problems. The structured but targeted nature of the intervention has been successful with all types of stressed and burdened caregivers, and with caregivers who are coping with varying challenges and levels of disease. For REACH II and REACH VA, intervention caregivers showed significant improvement in burden, depression, health and self-care, social support, and management of patient behaviors, caregiving frustrations that can lead to potential abuse, and gained an extra hour per day not spent in caregiving tasks (6-8).

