Hypothesis 1: Veterans of Caregivers who receive the intervention will have significant improvement in outcomes including the Expanded Disability Status Scale (EDSS), timed up and go test (TUGT), self-efficacy, and depression.

Hypothesis 2: Caregiver participants will have significant improvement in outcomes including depression, burden, anxiety, and number of Veteran MS problems and safety alerts reported.

Flowchart of REACH VA MS Intervention Protocol

INTERVENTION - OVERVIEW

The REACH VA Program for the MS Pilot Project is delivered in six sessions over a three month period. The Program Coach can conduct sessions with the Caregiver either face to face (home or facility) or by telephone or telehealth format.

The first component of the REACH VA Program is to assess risk in the caregiving situation, and then address risks by engaging the Caregiver in problem solving and skills building techniques. The program emphasizes safety, health, social support, Caregiver physical and emotional well-being, stress management, and problem solving.

- Caregivers are usually a family member or someone with a significant personal relationship who provides substantial, necessary, regular or long-term care for a Veteran with MS and is receiving services at the VA.
- The REACH VA Program can be delivered face to face (in the home or facility) or by telephone or telehealth. The Program Coach will provide Six Individual Sessions.
- Practical elements or tasks to be completed during the sessions include:
 - **Risk Assessment**
 - o Assess Caregiver risk in Session 1 using Risk Assessment.
 - o Program Coach uses this assessment throughout the REACH VA Program to target certain Care Recipient problems or safety issues and/or Caregiver centered problems related to health, physical and emotional well-being, and social support.
 - **Education Tasks**
 - o Provide general information about care recipient's condition (MS).
 - o Present safety materials.
 - o Present health care issues and explain the Health Guide.
 - o Present chapters in the Caregiver Notebook on Mobility and Wellness for the Veteran.
 - o Present Exercise brochures (Exercise as Part of Daily Life and Minimizing Your Risk of Falls) and review the Physical Therapy Exercise Plan.
 - **Problem Solving Tasks around Caregiver Concern**
 - o Problem solve to identify Target Problem.
 - o Introduce Problem Solving Plan.
 - o After initial plan, review and modify Problem Solving Plan.
 - o Introduce Mobility Plan

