Assessment & Session 1 Stress Management	Caregiver Assessment/Baseline Interview Ask CG to tell story Introduce Intervention Review Caregiver Notebook and Mobility Chapters Discuss effects of stress Introduce stress management technique, Signal Breath Discuss physical therapy appointment Obtain closure to session
Session 2 Problem Solving	Introduce Session Review/modify last session commitment - Signal Breath Provide general information about MS and Exercise Brochures Present safety material (including alerts if appropriate) Introduce health care issues and Health Guide Problem Solve – Target Problem #1 Obtain closure to session
Session 3 Problem Solving and Mobility	Introduce session Review/modify Problem Solving Plan #1 Make Commitment for Problem Solving Plan #1 Introduce Mobility and Wellness Chapters Problem Solve Mobility Plan Obtain closure to session

Session 4 Mood Management and Mobility	Introduce session Review/modify Mobility Plan and Check in on PT appointments Make Commitment for Mobility Plan #1 Review/modify Problem Solving Plan #1 Make Commitment for Problem Solving Plan #1 Introduce stress management technique, Mood Management Obtain closure to session
Session 5 Problem Solving or Mood Management	Introduce session Review/modify stress management technique, Mood Management Problem Solve – Identify Target Problem #2 or Work on another Mood Management Thought Record Offer stress management technique, Stretching, Power of Music, Guided Imagery, or Pleasant Events Obtain closure to session
Session 6 & Closure Problem Solving, Stress Management, Mood Management, and Mobility review	Introduce session Review/Modify Mobility Plan and Problem Solving Plan #1 and #2 Offer stress management techniques, Stretching, Power of Music, Guided Imagery, or Pleasant Events Present REACH VA Review Worksheet Obtain closure to session

PROGRAM COACH FORMS FOR INTERVENTION

The Program Coach must complete different forms throughout the intervention. Below is a brief description of each form:

- ❑ **Risk Assessment**: This form is used to record areas of risk in safety, caregiving skills, social support, Caregiver emotional and physical well-being, and Veterans problems/concerns. This form will be completed as part of the Baseline, 3, and 6 month interviews.

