Foreseeable Risk and Protection against risk. There are no physical risks to caregiver participants involved in this study. For therapeutic risks, during the individual session interventions some of the topics may be upsetting to participants. For Veteran participants, there is a risk of falling during the walk portion of the Expanded Disability Status Scale (EDSS). However, Veterans will be able to use any assistive devices normally required, and there are chairs and safeguards to stop the test if problems, such as light-headedness or fatigue occurs. The protocol allows for stops for rest.

For research risks, during data collection, caregiver participants may experience discomfort or fatigue in answering questions. Some questions may be upsetting to respond to. An additional research risk is loss of confidentiality or breach of identify. However, with the steps discussed below to remove PII in each data set and to identify participants with a coded ID before it is used for analysis, the likelihood of this happening is reduced. The results of this study may be published, but no specific information that could identify participants will be published. Participant records will not be revealed unless required by law.

The participant may experience discomfort or fatigue in answering questions. Some questions may be upsetting to respond to. During the baseline, End of Intervention (3 month), and 6 month data collection calls, a trained Program Coach will be able to help the participant should this occur. Also, the participant can take breaks or stop at any point. There is minimal risk of inadvertent release of personal information. However, care will be taken to secure all of the participant's information. Caregivers' and Veterans' research records will be labeled with a code number. The master key that links the names and the code numbers will be maintained in a separate and secure location in the data analyst's office, Building 1/Administration Building, Room CEG34. Only the project staff will have access to this information. Parts of the intervention sessions may be audio-taped strictly for research purposes and the caregiver's permission will be requested at the beginning of the session. The baseline, 3, and 6 month

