The Research Associate will read the Interviewer Instruction Manual (QxQs) in Manual of Operations Volume II. The Interviewer Instruction Manual will provide general guidelines and specific, question-by-question instructions for completing the REACH VA MS interviews and forms.

MEASURES AND TIME

CAREGIVER

Category	Name of Measure/Form	Citation/Source	Items	When
Demographic information	Participant demographics	various sources	15	Study entry
Health and health services		various sources	17	Study entry Follow up
Depression	Patient Health Questionnaire (PHQ-9)	(Kroenke et al., 2001)	9	Study entry Follow up
Anxiety	Generalized Anxiety Disorder (GAD-7)	(Spitzer et al., 2006)	7	Study entry Follow up
Social Support	Social Support	REACH II	10	Study entry Follow up
Burden	Zarit Burden Interview	(Bedard et al., 2001)	12	Study entry Follow up
Caregiving Tasks	Caregiving Tasks in Multiple Sclerosis Scale (CTiMSS)	(Pakenham, 2007)	24	Study entry Follow up
Risk Assessment	Risk Priority Inventory	Various sources	57	Study entry Follow up

VETERAN

Category	Name of Measure/Form	Citation/Source	Items	When
Demographic information	Participant demographics	various sources	11	Study entry
Health and health services		various sources	6	Study entry Follow up
Depression	Patient Health Questionnaire (PHQ-9)	(Kroenke et al., 2001)	9	Study entry Follow up
Impact on daily life	MS Impact Scale (MSIS-29)	(Riazi et al., 2002)	29	Study entry Follow up
Mobility	Timed Up and Go Test (TUGT)	various sources		Study entry Follow up
Self-Efficacy	MS Self-Efficacy Scale (MSSS)	(Rigby et al., 2003)	14	Study entry Follow up
Fatigue	Modified Fatigue Impact Scale (MFIS)	(Fisk et al., 1994)	21	Study entry Follow up
*Mobility/Neurological exam	Expanded Disability Status Scale (EDSS)	(Kurtzke, 1983)		Study entry Follow up

*Neurological exam completed by physician during clinic appointment.

OUTCOMES

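### The risk section rules out physical risk to Caregivers and omits the TUGT and home mobility work, and the plan describes no routine question on falls or Caregiver injury

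*Combined protocol and SAP*

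**What the plan says.** Under Foreseeable Risk and Protection against risk, the protocol says of Caregivers: "There are no physical risks to caregiver participants involved in this study". It adds that session topics and interview questions may be upsetting or tiring. For Veterans it says that "there is a risk of falling during the walk portion of the Expanded Disability Status Scale (EDSS"), and describes safeguards for that test: usual assistive devices, chairs and rest stops. No other physical risk is named. The Risk/Benefits Assessment paragraph gives only fatigue or distress from answering questions as examples.

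The intervention is described elsewhere. In the Objectives, and again under Goals of Intervention, "the intervention will target Caregiver participation in home-based Veteran mobility activities". The Intervention Overview instructs the Program Coach to "Present Exercise brochures (Exercise as Part of Daily Life and Minimizing Your Risk of Falls) and review the Physical Therapy Exercise Plan". In the session table, Session 3 includes "Problem Solve Mobility Plan", and Sessions 4 and 6 review that plan. The table under Measures and Time schedules the TUGT for Veterans at study entry and follow-up.

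**The concern.** A programme meant to help Veterans move more, with a family member taking part, has an obvious counterpart harm: Veterans may fall, and Caregivers may strain or injure themselves. A risk section that denies any physical risk to Caregivers, and confines falls to one clinic test, does not describe the study set out in the rest of the protocol. It matters even if no event occurs, because the consent process is to cover risks and discomforts.

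The second issue is measurement. Veteran outcomes include the TUGT and EDSS, and Objective 6 looks ahead to further research and implementation. If mobility results are carried forward without a count of falls and injuries collected the same way in every pair, readers will see one side of the balance only.

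**Working it through.** No arithmetic bears on this point, since the plan gives no fall or injury rate. The check sets the sections side by side.

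**Step 1. Physical activity in the study against the risk text.**

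| Activity | Where described | In the risk section? |
|---|---|---|
| EDSS walk (Veteran) | Measures and Time | Yes, with safeguards |
| TUGT (Veteran), entry and follow-up | Measures and Time | No |
| Home mobility activity (Veteran) | Objectives; Goals of Intervention; session table | No |
| Home mobility activity (Caregiver taking part) | Objectives; Goals of Intervention | No; physical risk to Caregivers is ruled out |

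One of four activities is covered. The TUGT is the plainest omission: it is a study procedure and a mobility test, like the one that is covered.

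**Step 2. Does the protocol recognise injury elsewhere?** The background says that training and including Caregivers "may help caregivers perform their tasks while avoiding injury to themselves and the MS patient". This presents training as protective and concerns caregiving tasks in general. It does not say the study causes injury. It does show that the authors regard injury to either member of the pair as possible in such tasks, which sits badly with an unqualified statement of no physical risk.

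**Step 3. Routes by which an event could be recorded.**

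| Route | What it covers | When | Falls or Caregiver injury named? |
|---|---|---|---|
| Risk Assessment/RPI (57 items) | Patient safety, Caregiver physical well-being, Veteran problems | Baseline, 3 and 6 months | Items not shown |
| Alert Form | Any event or alert | Baseline and during the study | No |
| Program Documentation Form | Significant change in status of either member | After each session and/or on notification | No |
| Session check-in | Physical therapy appointment, exercise plan, sessions attended | Each session | No |
| Health and health services items | 17 for Caregiver, 6 for Veteran | Entry and follow-up | Items not shown |
| Safety alerts outcome (Hypothesis 2) | Number reported | Baseline, 3 and 6 months | No |

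The Alert Form and the status-change record are places to write an event down once staff know of it. Neither is described as a prompt to ask. After the sessions, which are planned over three months, the next scheduled assessment is at 6 months. A participant who withdraws completes a discontinuation questionnaire and is not contacted again; no item on falls or injury is described for it.

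**Step 4. Reporting.** The Outcomes section lists no fall or Caregiver-injury count. Data Analysis describes repeated measures ANOVA on the outcome scores and no summary of adverse events.

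**The case against.** The strongest reply has three parts.

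First, the sessions consist of talk and may be held by telephone. The Coach reviews the exercise plan; the text does not say that this plan is carried out at home with the Caregiver. The falls brochure and the background sentence on injury describe mitigation, so the risk section may be incomplete without being refuted by the protocol's own evidence. This largely stands. Nevertheless, Caregiver participation in home mobility activity is a stated target of the intervention, and an absolute denial of physical risk cannot be squared with that.

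Second, a reader might infer that falls and Caregiver injuries would simply not be looked for. The documents do not support this. A risk paragraph does not determine what is recorded, and Step 3 lists several routes. The RPI items, the Alert Form, Manual of Operations Volume III (which covers alert procedures), the consent form and a short part of the protocol were not available. Any of these might contain the questions.

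Third, this is a single-group pre-post feasibility study. Falls in Veterans with MS cannot be attributed to the programme without a comparison, and added questions would not change that. This stands in full and limits what the counts can be used for. It does not remove the case for collecting them consistently.

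**Conclusion.** The risk section and the intervention description do not agree and must be reconciled. The unqualified statement about Caregivers does not fit the home mobility component, and the Veteran text omits both the TUGT and home activity. That part rests on the text alone.

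The measurement part is narrower. The available text describes general capture routes, but no routine question on Veteran falls or Caregiver injury and no planned summary of either. It assumes that the RPI items and the alert procedures do not already ask; if they do, only the reporting needs attention.

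The size cannot be given as a number. An upper limit on the fall rate after zero observed falls would reflect the number of Veterans only, and would say nothing about this gap. A reader might also infer that the programme raises the fall rate. Nothing in the documents shows this, and the design could not test it. This is a cheap improvement to disclosure and harm ascertainment and does not threaten the main analyses.

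**What to change.** 1. Revise the risk section so that it covers the TUGT and home mobility activity for Veterans, and physical strain or injury for Caregivers. Bring the Risk/Benefits Assessment paragraph into line, and check the consent form against both.
2. Check the RPI items and the alert procedures. Unless they already ask, add two fixed questions on Veteran falls and on Caregiver injury since the last contact. The Program Coach asks them at each session and the interviewer asks them at baseline, 3 months and 6 months. State the look-back period for baseline, where there is no earlier contact.
3. Record the answers on the existing Alert Form, including a negative answer, so that a zero can be told from a question not asked. The form is listed among the Program Coach's forms, so the interviewer would need to use it as well.
4. Report the counts descriptively beside the mobility outcomes, with the number of pairs asked at each contact, and without attributing events to the programme.

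Cost: 1 baseline + 6 sessions + 2 follow-ups = 9 contacts, or 8 if Session 1 is held at the baseline visit. At an assumed one minute each, that is 8 to 9 minutes per pair, or 25 × 8 = 200 to 25 × 9 = 225 minutes over 25 pairs. The risk statement will read less favourably. No visit, outcome measure, treatment element or sample size changes.
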